1.0 Research Introduction

1.1 Purpose/Specific Aims

We propose to compare the use of a nerve stimulator for ultrasound-guided supraclavicular block (test treatment) to the standard treatment where nerve stimulators are not used (standard treatment) for patients undergoing upper extremity surgery. The block is routinely performed to provide analgesia to the upper limb prior to surgery. The hypothesis is that using the nerve stimulator in conjunction with the ultrasound will provide a more accurate method of performing the supraclavicular block. This should result in better outcomes, including improved onset time of analgesia and improved pain control during and after surgery. There is no increased risk to the patients participating in the test treatment group compared to those in the standard treatment.

A. Objectives

The objectives of the study are to demonstrate a difference in quality and effectiveness of analgesia (completeness of pain relief), or extended duration of block as a result of the addition of a nerve stimulator in the performance of the block.

B. Hypotheses / Research Question(s)

The hypothesis is that using a nerve stimulator will improve the effectiveness, quality, and outcome of ultrasound guided supraclavicular blocks.

1.2 Research Significance (*Briefly describe the following in 500 words or less*):

Supraclavicular (above the collarbone) block is a popular anesthetic technique for upper extremity surgery. Historically, this technique utilized anatomically guided needle placement for proper distribution of the anesthetic, but it carried the risk, among others, of pneumothorax. This risk was significantly reduced by the use of ultrasound guidance for needle placement. We propose to further improve the efficacy of this now standard regional block technique by using a nerve stimulator in addition to ultrasound visualization.

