- In the Test Group, the Braun DIG –R-C Stimuplex blockade monitor system will be initially set at 1 milliamp as the needle approaches this area. As the proximity of the tip of the needle to the components of the brachial plexus becomes evident by ultrasound approximation and the stimulation pattern of the hand and wrist, the output of the system will be reduced to .3-.5 millamps. In the absence of paresthesia and after negative aspiration, the 40 ml of local anesthetic block will be administered.

- Description of Braun DIG-R-C Stimuplex Blockade Monitor
This monitor is a nerve stimulator used for locating peripheral nerves in regional anesthesia and pain therapy. It is a class IIa medical device. During the performance of a regional block, as the needle tip approaches the nerve, there appears a muscle twitching in the appropriate muscle group.. This is not painful to the patient. The stimulus is adjusted to estimate the proximity of the needle to the nerve bundle. As the output of the impulse generator is turned lower, there will still be twitching at close range to the nerve. This is the ideal injection point as the device indicates that the stimulus is so low that the needle tip is not within the nerve sheath itself, but instead close to the nerve. This is one way to safely determine how close to a nerve the needle is, without entering the nerve. Only the subsequently injected medicine will enter the nerve, providing an additional element of safety.

B. Data point collection

- During the performance of the block, when the stimulation pattern is still evident at the lower output of the block monitor, the pattern of the movement of the hand will be recorded
- Patients in both groups will be assessed every 5 minutes for the quality of the block, ending at 20 minutes post block. This will involve 4 data points.
- Assessment includes (**See data collection sheet**):
 - response to strength testing of the upper extremity
 - response to hot and cold discrimination with an alcohol pad

response to fine touch provocation

Data points for all subjects will be taken during and after surgery to assess:

1. Speed of onset of the block
(At 5 min intervals, subjects will be asked to flex their arm against gravity to determine onset of the block).
2. Assessment of intraoperative quality of the block

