(Beginning 5 minutes after the placement of the local anesthetic, and at 5 min intervals, subjects will be asked to distinguish hot and cold and fine touch in the dermatomes of the shoulder and hand. They will have the opportunity to express inadequacy of the block at which time they will receive additional anesthetic in the form of IV supplement or general anesthesia.
 - Duration of block
(At 30 min intervals post op, subjects will be evaluated for sensory and motor function as compared to the contralateral (opposite) arm, or compared to their preoperative evaluation. Two evaluations will be done, each taking approximately 5 minutes

C. Duration of study and length of time the participant will participate

The duration of the study will be 2 years

The study participant will be assessed during the injection and for 20 minutes after the injection for the block itself and the duration of the entire research data collection would be thirty minutes

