1.5 Sample Size Justification

For investigation of improved onset time of analgesia, a smaller sample of 34 subjects in each group (N1=34, N2=34) will be sufficient to maintain 80% power and 0.05 alpha level of statistical significance to show 35% decrease in onset time from 20 min to 13 min (effect 0.7) to achieve the Supraclavicular Block with combined use of ultrasound and nerve stimulator.

According to classic studies Williams et al 2003 (doi: 10.1213/01.ANE.0000086730.09173.CA), onset of sensory block parallels onset of partial motor blockade and was 14+/-6 vs 18+/-6 min for ultrasound-guided vs nerve-stimulator guided supraclavicular block.

This was calculated using the power calculation for sample size for continuous outcomes as the dependent variable and two independent samples for the independent variable.

Accrual rates should be about 50% of the available upper extremity renal transplant / vascular graft procedures which should happen at a rate of 2-4 per week.

However, for observation of qualitative data, we decided on a sample size of 100 (N1=50, N2=50).

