1.6 Study Variables

A. Independent Variables, Interventions, or Predictor Variables

The only difference (the intervention) between the study groups involves the use of the nerve monitor during the performance of the block

The performance of the block with both the ultrasound and the nerve monitor is in excess of the standard of care which utilizes the ultrasound alone , but the needle used for the block is the same in both groups. It is the Stimuplex Teflon coated needle which can be used with or without application of the nerve monitor function

B. Dependent Variables or Outcome Measures

I have expectations that the use of the nerve block monitor will result in a faster speed of onset of the block as the performance characteristics of the block placement relative to the target nerve may be improved.

Dependent variable would be success of the block as measured objectively by speed of onset.

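### The stated objective does not name onset, the only outcome with a power calculation; no outcome is labelled primary, and the listed t-test does not fit onset as it is recorded

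*Protocol*

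**What the plan says.** **Objective.** Protocol 1.1A: "The objectives of the study are to demonstrate a difference in quality and effectiveness of analgesia (completeness of pain relief), or extended duration of block". Hypothesis 1.1B speaks of effectiveness, quality and outcome and does not mention onset.

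**Purpose paragraph, just above 1.1A.** "This should result in better outcomes, including improved onset time of analgesia and improved pain control during and after surgery". Onset appears here as an expected benefit.

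**Dependent variable, 1.6B.** "Dependent variable would be success of the block as measured objectively by speed of onset". No other dependent variable is named.

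**Sample size, 1.5.** "For investigation of improved onset time of analgesia, a smaller sample of 34 subjects in each group" gives 80% power at alpha 0.05 for a fall from 20 to 13 min (effect 0.7). Section 6.1B repeats 20 and 13 min, adds an SD of 10, prints a ratio of 0.65 and arrives at 33 per group. The larger total is explained in 1.5 only by this: "However, for observation of qualitative data, we decided on a sample size of 100 (N1=50, N2=50").

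**Measurement, 1.3B.** For onset: "At 5 min intervals, subjects will be asked to flex their arm against gravity to determine onset of the block". For timing: "Patients in both groups will be assessed every 5 minutes for the quality of the block, ending at 20 minutes post block". Intraoperative quality includes patients saying that the block is inadequate, whereupon "they will receive additional anesthetic in the form of IV supplement or general anesthesia". Duration rests on two post-operative evaluations at 30-minute intervals.

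**Analysis.** Protocol 6.1A lists descriptive statistics, t-tests and ANOVA without assigning any of them to an outcome. It says the results will inform whether a larger study is supported. SAP sections 6.2, 9.6 and 11.1 are still template instructions, so they do not settle the matter.

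**The concern.** A reader who takes 1.1A as the statement of what the trial must show would judge it on quality or on duration. Neither has an effect size or a power statement, and the word joining them does not say which carries the claim. A reader who takes 1.5 and 1.6B would judge it on onset. With nothing labelled primary, that choice can be made after the results are known.

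There is a second, linked problem. If onset is the intended primary outcome, the test listed for it needs a number for every patient. The recording scheme gives only 5, 10, 15 or 20 minutes, or no onset by the last assessment. The last assessment falls at the assumed control mean, so missing values would be common and would fall more often in one group than in the other.

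Onset is also described in two ways: as onset of analgesia in 1.5 and as an arm-flexion test in 1.3B.

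**Working it through.** **1. Which outcome does the 80% belong to?** Inputs: difference 20 − 13 = 7 min (1.5, 6.1B), SD 10 (6.1B), alpha 0.05, power 0.80. Sidedness is not stated; two-sided is assumed because it reproduces the plan's figures.

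n per group = 2(1.960 + 0.842)² / (7/10)² = 2 × 7.849 / 0.49 = 32.04, rounded up to 33. The t-test version gives 33.02, rounded up to 34. Both printed figures (33 and 34) are reproduced; a one-sided test would give 26. The stated power therefore comes from the onset calculation alone.

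The ratio printed in 6.1B does not match its own inputs: 7/10 = 0.70, not 0.65. A true 0.65 would need 38 to 39 per group.

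**2. Power for onset at the planned size, if onset were an exact time** (two-sample t-test, two-sided 0.05):

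| Per group | effect 0.70 | effect 0.65 |
|---|---|---|
| 33 | 80.0% | 73.9% |
| 34 | 81.2% | 75.2% |
| 50 | 93.4% | 89.6% |

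**3. Quality and duration.** The documents give no rate, SD or effect for either, so no power can be derived. For scale only, take an assumed yes/no quality outcome with 50 per group (chi-square, exact enumeration): 73% power for 70% vs 90%, 30% for 80% vs 90%, 14.5% for 90% vs 95%. The widest 95% CI half-width for a difference in proportions is 1.96 × √(2 × 0.25/50) = 0.196, about 20 percentage points.

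**4. Patients with no onset value at 20 minutes.** This is P(T > 20) for an onset time T. The documents give no shape, so three are assumed. Under the normal shape, controls have 1 − Φ((20 − 20)/10) = 50.0% and test patients 1 − Φ((20 − 13)/10) = 24.2%.

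| Shape | Control (20, SD 10) | Test (13, SD 10) | Control (14, SD 6) |
|---|---|---|---|
| normal | 50.0% | 24.2% | 15.9% |
| gamma | 43.3% | 19.7% | 15.3% |
| lognormal | 40.7% | 16.5% | 14.1% |

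The last column uses the 14 ± 6 min that 1.5 itself cites for ultrasound-guided block, which is the control technique here.

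**5. Does a rank test on the recorded categories cost too much power?** Mann-Whitney with tie correction on 5, 10, 15, 20 or none by 20; 20,000 simulated trials per shape; 50 per group:

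- 20 vs 13 min, SD 10: about 89%, 98% and 99% (normal, gamma, lognormal).
- Ratio 0.65, normal shape: about 84%.
- Control 14, SD 6, and an assumed 11 in the test group: about 65–81%.

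**The case against.** The strongest reply is that this is incomplete drafting and not a contradiction. Onset is named in the purpose paragraph of the same section, and 1.6B presents speed of onset as the measure of block success, which could be read as the effectiveness in 1.1A. That has some force: onset is not missing from section 1.1 as a whole. But 1.1A explains effectiveness as completeness of pain relief, which is not speed, and no section labels a primary outcome.

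It can also be said that the reason given for 50 per group is descriptive and claims no power, so the lack of a calculation there is not an error in itself. That is right. The point is only that the larger number does not extend the power statement to quality or duration.

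The rank test is one choice among several; an interval-censored or discrete-time comparison would also handle patients without onset. That stands too.

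The three SAP sections are blank because the whole SAP is an unfilled template. Their blankness is why the gap stays open, not a further error.

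A reader might infer more than the documents support:

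- **That the trial is too small.** On the plan's own inputs it is not: 50 per group gives about 93% for an exact onset time.
- **That 50 per group is enough regardless.** This holds only for 20 vs 13 min, SD 10; the cited 14 ± 6 leaves less room for a reduction.
- **That a particular familywise error rate follows.** The plan states no multiple-test rule from which to compute one.

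**Conclusion.** The point holds as a mismatch between objective and power, with a missing label. The stated 80% (33 to 34 per group) applies to onset, which 1.1A does not name; quality and duration, which it does name, have no power statement. Since nothing is ranked, a positive result could be claimed on any of the three.

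The t-tests in 6.1A do not suit onset as recorded. About 41–50% of controls and 17–24% of test patients would lack a value under 20 vs 13 min, SD 10, and about 14–16% of controls under 14 ± 6. These shares rest on assumed distribution shapes. The normal shape is rough, since it puts about 10% of test patients below zero. The finding that the loss is substantial and unequal under the plan's own inputs does not depend on which of the three shapes is used.

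This is worth correcting before outcomes are compared. It does not call the sample size into question on the plan's assumptions.

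**What to change.** 1. Reword 1.1A along these lines: *The primary objective is to compare onset time of the block between groups (two-sided alpha 0.05). Secondary objectives are block quality to 20 minutes, intraoperative quality including use of supplementary IV or general anesthesia, and block status at the two post-operative evaluations.* Bring the purpose paragraph, 1.1B, 1.5, 1.6B, 6.1 and SAP 6.2, 9.6 and 11.1 into line.
2. Use one onset definition throughout: the first 5-minute assessment at which the patient cannot flex the arm against gravity (the 1.3B onset test), recorded as 5, 10, 15, 20 or not by 20. If sensory onset is meant, name one sensory sign from 1.3B instead.
3. In 6.1A and SAP 11.1, replace the t-test for onset with Mann-Whitney on these ordered categories, or another method that handles patients without onset by 20 minutes. Report an effect estimate with 95% CI, for example the probability of earlier onset and the difference in the proportion with onset by 20 minutes.
4. Report quality and duration as between-group differences with 95% CIs and no confirmatory claim. That suits the purpose in 6.1A of deciding on a larger study.
5. In 1.5, state that the power is for onset only and is conditional on 20 vs 13 min, SD 10 (t-test on an exact time: about 81% at 34 and 93% at 50 per group), and that quality and duration are not powered. Correct 0.65 in 6.1B to 7/10 = 0.70. Keep simulated power under assumed shapes out of the protocol.

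**Cost.** Rewording several protocol passages and completing three SAP sections. Sample size and procedures do not change, nor do the data collected, provided the data sheet (not shown) holds the 1.3B items. The price is that quality and duration lose any stand-alone significance claim.

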6.0 Research Data Protection and Reporting

6.1 Data Management and Confidentiality

A. Aggregated and de-identified data from paper documentation will be input into an SPSS data file, secured on a password-protected computer kept in the P.I.'s locked office and secured by Rutgers-RWJMS access code. Group data will be analyzed using descriptive statistics, t-tests and ANOVA. Results will be evaluated by the P.I. in consort with the co-investigators to determine whether this clinical trial supports a larger study.

B. *Difference in time of supraventricular block with ultrasound compared to without is 20 and 13 min, respectively with a standard of deviation of 10. This gives an S/N ratio of 0.65. The alpha will be set to 0.05, the power will be set to 0.80. This gives a necessary sample size of 33 for each group. 50 in each group will be sufficient.*

C. **Separation of identifiers will be used for each patient. Data will be stored on a secure cloud.**

D. Data entry will be handled by the PI. 10% of the flow sheets will be reentered by a second clerk, [name], who is a member of the research team and the entries compared for accuracy. If there is more than a 1% difference in data entry, the data will be corrected and the test repeated with another 10 percent of the remaining flow sheets. This process will be repeated until there is a less than 1% disparity between the two data entry processes.

E. All data will be gathered using the same data form (Appendix A). Flow sheets of data will be kept in the P.I.'s locked office. Subjects will be identified by a study number and a copy of the data flow sheet given to the data entry clerk. Data analysis of the confidential data set will be performed by the fellows.

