9.6 Multiple Testing

(ICH E3; 9.7.1, 11.4.2.5. ICH E9; 2.2.5)

This section can be copied from the protocol, if available.

Statistical Analysis Plan: Does the use of nerve stimulator improve the outcome of ultrasound guided supraclavicular block (anesthesia) for upper extremity surgery?

In a confirmatory trial, the choice of sample size will be justified in terms of the power, which focuses on a single analysis, which in turn focuses only on one primary endpoint. This means there should only be one primary endpoint.

However, exceptions to this maxim do occur. In such circumstances the most acceptable statistical methodology is to either combine the co-primary endpoints through a deterministic function into a single endpoint or adopt a formal closed-testing procedure that examines a variety of hypotheses in such a way that preserves the overall significance level of the analyses; for example, Bonferroni adjustments of the nominal significance level, or gate-keeping approaches to a pre-specified order of hypothesis tests.

In trials that are focused on learning and hypothesis generation, the preservation of the overall significance level is of lesser importance, however there should be a statistical discussion that reflects awareness of the issues, and the analyses should present confidence intervals rather than p-values.

Identical issues arise if there are:

- more than two treatment groups,
- subset analyses,
- multiple time points,
- multiple methods of analysis,
- sensitivity analyses for missing data.

10 Summary of Study Data

Specify the method of describing the study data that will be presented in the final study report. This section provides a general overview of the methods. If any of the items require a unique approach that differs from the general overview, then it should be noted in the appropriate section.

Specify

- How summary tables will be structured (e.g. columns for each treatment and overall in the order: Placebo, Experimental Low Dose, Experimental High Dose, All Subjects.)
- Descriptive or summary statistics that will be displayed for continuous data and for categorical data.
- The analysis populations upon which the tables and figures will be based.

Example:

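### The objective in Protocol 1.1A is met by quality 'or' duration and omits onset, the only powered outcome, and neither document sets a primary endpoint, testing order or multiplicity rule

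*Protocol*

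**What the plan says.** - **Objective.** Protocol 1.1A sets out to "demonstrate a difference in quality and effectiveness of analgesia (completeness of pain relief), or extended duration of block". Onset does not appear in it.
- **Expected benefits.** The purpose paragraph of 1.1 is wider: "This should result in better outcomes, including improved onset time of analgesia and improved pain control during and after surgery".
- **Dependent variable.** Protocol 1.6B: "Dependent variable would be success of the block as measured objectively by speed of onset". The word primary is not attached to this or to any other outcome.
- **Power.** Section 1.5 says that 34 per group "will be sufficient to maintain 80% power and 0.05 alpha level of statistical significance to show 35% decrease in onset time from 20 min" (the target being 13 min). Section 6.1B repeats the onset calculation: "The alpha will be set to 0.05, the power will be set to 0.80". These are the only places where a significance level is set for this trial, and both concern onset. The increase to 50 per group is attributed to qualitative data, with no power given for them.
- **Measurements.** In 1.3B, block quality is checked by strength, hot/cold and fine touch every 5 minutes up to 20 minutes ("This will involve 4 data points"). Duration is judged post-operatively on sensory and motor function ("Two evaluations will be done, each taking approximately 5 minutes").
- **Analysis.** Section 6.1A names descriptive statistics, t-tests and ANOVA for group data. It does not link them to outcomes or give an order or an adjustment.
- **SAP.** Sections 6.2 (endpoints), 9.6 (multiple testing) and 11.1 (primary analysis) still hold the template's instructions. The template text in 9.6 says of a confirmatory trial: "This means there should only be one primary endpoint". It allows a formal multiple-testing procedure as the exception.

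**The concern.** The objective works as a success rule with two routes, and neither route is the outcome for which the trial was sized. Suppose the stimulator does nothing, onset shows no difference, and one quality or duration comparison is significant by chance. The trial has then met 1.1A as written. Nothing in either document stops that result being reported as the demonstration the objective asks for, and no error rate attaches to it.

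This is a fault in the success rule as well as missing detail: 1.1A points to one set of outcomes, while 1.5, 1.6B and 6.1B point to another.

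**Working it through.** **The plan's own figure.** Inputs from 1.5 and 6.1B: 20 vs 13 min, SD 10, alpha 0.05, power 0.80.

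n per group = 2 × (1.960 + 0.842)² × (10/7)² ≈ 32.04, rounded up to 33. The t-test version gives 33.02, so 34. Both stated figures (34 in 1.5, 33 in 6.1B) are reproduced. A one-sided 0.05 would give 26. The documents do not state sidedness, but the stated sizes fit a two-sided test, and this is assumed below.

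**What level applies to quality and duration?** None is stated. The rest of the working is conditional: it asks what follows if the one stated level, two-sided 0.05, is applied to each outcome and any significant result counts.

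**Independent outcomes, no true effect:**

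- The two 'or' outcomes, difference in either direction: 1 − 0.95² = 0.0975.
- The same two, read literally, so that duration counts only if extended (0.025 in that direction): 1 − 0.95 × 0.975 = 0.074.
- Onset, quality and duration, either direction: 1 − 0.95³ = 0.143.
- The same three, false benefit only (0.025 each): 1 − 0.975³ = 0.073.

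**Correlated outcomes.** The documents give no correlations, so a range is assumed. Test statistics were simulated as equicorrelated normals, Z = √r·G + √(1−r)·E, with 2,000,000 draws:

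| Family | r = 0 | r = 0.5 | r = 0.8 |
|---|---|---|---|
| Two 'or' outcomes, either direction | 9.75% | 9.0% | 7.8% |
| Three outcomes, either direction | 14.3% | 12.5% | 9.8% |
| Three outcomes, benefit only | 7.3% | 6.3% | 4.9% |

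The reference value is 5% for the first two rows and 2.5% for the third.

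**Onset as single primary endpoint.** Its error stays at 5% (2.5% in the favourable direction). With 50 per group, power for 20 vs 13 min is 93.8% (normal) or 93.4% (t).

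**The case against.** **Onset is already the primary endpoint in all but name.** It is the only powered outcome and the declared dependent variable. On that reading the primary error is 5% and quality and duration are supportive. This is a fair reading of 1.5 and 1.6B, and the fix adopts it. It does not rescue 1.1A, which leaves onset out and can be met without it.

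**The trial is partly exploratory.** Section 6.1A says the results will help decide whether a larger study is supported, and the template text in SAP 9.6 treats control of the overall level as less important in hypothesis-generating trials. That lowers the stakes. But 1.1A speaks of demonstrating a difference and 6.4 plans publication. The same template text asks exploratory trials to discuss the issue and to present confidence intervals rather than p-values. Neither document does so.

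**Stronger readings that the documents do not support:**

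- A reader might infer that the plan tests every outcome at an unadjusted 0.05. It does not say so. The level is given for onset alone, and the enlarged sample for qualitative data fits descriptive reporting equally well. What is documented is the absence of a rule.
- A reader might take 14.3% as the chance of a false claim of benefit. It counts false differences in either direction. The benefit figure is 7.3% or less: roughly two to three times the one-direction 2.5%, but not far above 5%.
- A reader might multiply three responses by four checks and count twelve tests. No such tests are planned. Checks five minutes apart in one patient are also far from independent, and arm strength overlaps with the measure of onset.

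**Conclusion.** The point holds as a mismatch between the objective and the powered outcome, combined with no multiplicity rule. The objective can be satisfied by either of two unpowered outcomes whatever onset shows.

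Under the assumed two-sided 0.05 per outcome, the chance of at least one false difference is 9.75% for the two 'or' outcomes if independent, about 9% at correlation 0.5, and 7.4% if independent when duration counts only if extended. For onset, quality and duration together it is 14.3% if independent and about 12.5% at correlation 0.5. For false benefit alone, the three outcomes give 7.3% if independent and 6.3% at correlation 0.5, against 2.5%.

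These sizes depend on the assumed level, sidedness and correlations. The absence of a labelled primary endpoint, a testing order and an adjustment does not. The trial can be run as it stands, but a positive statement under 1.1A would have no defined error rate, so the text should be changed before analysis.

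**What to change.** 1. Name onset as the single primary endpoint, tested at two-sided 0.05.
2. If it is significant, test one prespecified quality measure per patient at 0.05. If that is significant, test one prespecified post-operative residual-block measure at 0.05. Stop at the first non-significant result. This holds the overall two-sided error at 5%.
3. Report all other responses and time points with 95% confidence intervals and no claim of significance.
4. Replace the 'or' in 1.1A so that the objective follows this order, and carry the same text into Protocol 6.1 and SAP 6.2, 9.6 and 11.1.

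If Holm's procedure is preferred, it must cover all three outcomes. Applied to quality and duration alone, with onset tested separately at 0.05, it leaves 1 − 0.95 × 0.975² = 9.7% if independent. Over three outcomes the smallest p-value must fall below 0.05/3 = 0.0167. At that level, 50 per group still gives onset 86.6% power (normal) or 85.4% (t).

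Cost: wording only, with no more patients or data. Under the fixed order, power for onset is unchanged, but a quality or duration claim cannot be made if onset is not significant.
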